#### **7.4.2.1.2 Infusion Interruptions/Re-Start/Dosage Adjustments due to Adverse Events**

##### **7.4.2.1.2.1 General Guidelines**

Subjects should be assessed for adverse events at each visit. The severity of the adverse event will be graded using the CTCAE version 5.0 ([Section 12.4](#)), with the exception of CRS, which must be graded using the criteria referenced in the publication by [Lee et al, 2014](#) (see [Table 7-3](#)) and TLS, which must be graded according to the Cairo Bishop criteria referenced in the publication by [Coiffier et al, 2008](#) (see [Section 12.12](#)).

Infusion modification and dose reduction due to an adverse event will be performed according to the instructions described below and outlined in [Table 7-1](#) and [Table 7-3](#).

Infusion interruptions for other reasons need to be discussed with the Amgen medical monitor.

If infusion interruptions of < 14 days occur within a cycle the cycle will be resumed. The counting of the cycle days will not be stopped with an infusion interruption (eg, if the infusion is stopped on cycle day 5 and resumed 5 days later, the day of re-start is cycle day 10).

Following an infusion interruption with < 7 days remaining for infusion after resumption of the cycle, the last treatment days can be skipped and treatment will be continued with the next cycle after a 2-week infusion free interval.

However, treatment should not be given for < 14 days per cycle. An infusion interruption of more than 2 weeks or several interruptions exceeding a total of 14 days of treatment per cycle due to serious adverse events/adverse events require permanent treatment discontinuation.

Please note: the guidance in [Section 7.4.2.1.2](#) does not apply to the treatment holiday described in [Section 7.1.1.2](#).

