##### 7.1.1.2 AMG 420 Dosage, Administration, and Schedule

AMG 420 will be administered as a cIV infusion. A treatment cycle consists of a 4-week infusion period followed by a 2-week infusion-free interval prior to the following treatment cycle (phase 1b, monotherapy). Refer to [Section 7.4.2.1.2.2](#) for treatment delays due to AEs.

#### Cohort 1

Subjects in cohort 1 will receive a dose of 400 µg/day starting on day 1 of each treatment cycle. If a dose step is determined to be needed after DLRT review of all

available safety data, the initial dose will be 200 µg/day for the first 3 days of treatment cycle 1. On day 4 of cycle 1 and for the remainder of cycle 1, the dose for cohort 1 will then be escalated (dose step) to 400 µg/day. From cycle 2 onwards, the dose will remain at 400 µg/day, no dose step will be required.

#### Cohort 2

Subjects in cohort 2 will receive a dose of 200 µg/day for the first 3 days of treatment cycle 1. On day 4 of cycle 1 and for the remainder of cycle 1, the dose for cohort 2 will then be escalated (dose step) to 600 µg/day. From cycle 2 onwards, the dose will remain at 600 µg/day and no dose step will be required. See [Section 12.11](#) for procedures.

Subjects with EM disease will be able to enroll into cohort 2 after the safety evaluation is complete for 3 subjects with EM disease treated at 400 µg/day (cohort 1).

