#### 7.4.2.1.2.4 Dosage Adjustments/Re-Start at a Lower Dose Level/ Dose-Escalation

For adverse events for which re-start of treatment is allowed according to the guidelines outlined in [Table 7-1](#) and [Table 7-3](#), treatment may be resumed under medical supervision at the same dose or a lower dose.

Premedication as described in [Section 7.1.4](#) must be administered prior to re-start, if applicable.

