##### Dose-escalation:

Dose-escalation is allowed with start of the next treatment cycle if treatment is well tolerated and escalation is appropriate according to the investigator's judgement. In addition to the assessments required as per Schedule of Activities (see [Section 2.2](#)), a

neurological examination should be performed before dosing in case the infusion interruption was due to a neurologic event.

The subject should be hospitalized for at least 48 hours after dose-escalation (see also [Section 7.1.1.4.1](#)).

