2	Symptoms require and respond to moderate intervention 
 
• Oxygen requirement < 40% (for room air, oxygen saturation 90% or less), OR
 
• Hypotension responsive to fluids or low dose of 1 vasopressor, OR
 
• Grade 2 organ toxicity or grade 3 transaminitis per CTCAE criteria
 
	Immediately interrupt AMG 420 until event has improved to CRS grade ≤ 1, but for no less than 72 hours.	Administer: 
 
• Symptomatic treatment (eg, paracetamol/acetaminophen for fever)
 
• Supplemental oxygen when oxygen saturation is < 90% on room air
 
• Intravenous fluids or low dose vasopressor for hypotension when systolic blood pressure is < 85 mmHg. Persistent tachycardia (eg, > 120 bpm) may also indicate the need for intervention for hypotension.
 
 Monitor for CRS symptoms including vital signs and pulse oximetry at least Q2 hours for 12 hours or until resolution to CRS grade ≤ 1, whichever is earlier. Investigators may also use tocilizumab c as an additional therapy in this setting at a dose of 4-8 mg/kg as a single dose, particularly if CRS does not improve to grade ≤ 1 within 4 hours after dose interruption. For subjects with extensive co-morbidities or poor performance status, manage per grade 3 CRS guidance below.	
 
• Re-start possible, if successfully managed and improvement to CRS grade ≤ 1 within 7 days,
 
• Consult with Amgen medical monitor first.
 
• Hospitalization: 48 hours
 
• In the event of 2 consecutive cases of CRS of grade 2, consider reducing dose to 200 µg/day for subjects originally receiving 400 µg/day or 400 µg/day for those originally receiving 600 µg/day
 
• Additional measures: additional assessments and premedication as indicated in Sections 7.4.2.1.2.3/7.4.2.1.2.4
 
	
 
• If there is no improvement to CRS ≤ grade 1 within 7 days
 
• If interruption is > 14 days
 
• In case of repeat grade 2 event despite dose reduction
 

Footnotes defined on last page of table.

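### Cohort 2 DLT evaluability requires no 600 µg/day exposure, so a subject held in the 200 µg/day run-in can count as DLT-free in the 600 µg/day cohort

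*Protocol*

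**What the plan says.** **Dosing.** Protocol 7.1.1.2 gives cohort 2 a run-in of 200 µg/day for three days, and then: "On day 4 of cycle 1 and for the remainder of cycle 1, the dose for cohort 2 will then be escalated" to 600 µg/day. From cycle 2, "the dose will remain at 600 µg/day and no dose step will be required".

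**Holds.** Under protocol 7.4.2.1.2.1, "Infusion modification and dose reduction due to an adverse event will be performed according to the instructions described below" and in Tables 7-1 and 7-3. During a hold, "The counting of the cycle days will not be stopped with an infusion interruption".
- Grade 2 CRS (Table 7-3): the infusion stops until improvement, "but for no less than 72 hours". Restart requires improvement to grade 1 or less within 7 days.
- Neurotoxicity of grade 3 or more, or a rise from grade 0 to grade 2 (Table 7-1): immediate interruption, then restart at 200 µg/day.

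**Dose at restart.** Protocol 7.4.2.1.2.4 says "treatment may be resumed under medical supervision at the same dose or a lower dose". A lower-dose restart runs to the scheduled end of that cycle. The only escalation timing in that section is: "Dose-escalation is allowed with start of the next treatment cycle if treatment is well tolerated".

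**Who counts.** Protocol 7.4.1 sets the DLT period as four weeks of cycle 1 starting on day 1. A subject is evaluable after completing it or after having a DLT. Protocol 5.2.1 makes a subject non-evaluable only for stopping treatment early for a reason other than a DLT, and SAP 6.2 agrees. SAP section 5 requires a DLT to start within 28 days of first dose. Table 5-1 counts treated subjects, and SAP 9.6.2 reports DLTs by dose level. None of these sets a minimum exposure at 600.

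**The concern.** Protocol 5.4 names establishing the safety and tolerability of 600 µg/day as a main purpose of the study. The hold rule in Table 5-1 and the DLT rate for cohort 2 serve that purpose only if the people in the denominator received 600. As the rules stand, a subject whose DLT window was spent at 200 adds one to the 600 denominator and, without a DLT at 200, nothing to the numerator. The hold rule works on very small counts, so one such subject can change its answer.

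There is also a safety side. If the first 600 exposure comes at cycle 2, it falls outside DLT counting. It would also have a shorter observed stay: for escalation after a restart, "The subject should be hospitalized for at least 48 hours after dose-escalation", whereas the planned step leaves 72 hours of the 6-day cycle 1 stay.

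**Working it through.** **1. The plan's own figures.** Protocol 10.1 gives 65% to 89% as the chance of seeing at least one event in 10 subjects at true rates of 10% to 20%. 1 − 0.9^10 = 0.651 and 1 − 0.8^10 = 0.893, so it reproduces. Table 5-1 also reproduces from protocol 10.3 (Beta(1,1) prior; intervals 0–20%, 20–33%, above 33%; posterior probability divided by interval width). The fewest DLTs for which over-dosing has the largest mass are 2 at n ≤ 4, 3 at n = 5–6 and 4 at n = 7–8.

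**2. Can the window pass with no 600 exposure?**
- *Neurologic event, grade 0 to 2, on days 1–3.* Table 7-1 requires a hold and a restart at 200, and 7.4.2.1.2.4 keeps a lower-dose restart to the end of the cycle. Grade 2 is below the grade 3 threshold for a non-hematologic DLT in 7.4.1. Result: 0 days at 600, no DLT, evaluable.
- *Grade 2 CRS on days 1–3.* If the hold starts at hour h, with 0 ≤ h < 72, restart is at hour h + 72 or later, so on cycle day 4 or later. The scheduled step time has then been reached or passed. Restart is at the same or a lower dose, that is 200. No text says when the missed step follows.

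Planned exposure in 28 days is 3 × 200 + 25 × 600 = 15,600 µg. For a CRS hold of H days:

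| Reading | H = 3 | H = 7 |
|---|---|---|
| Run-in completed, then step: 600 + (25 − H) × 600 | 22 days at 600; 13,800 µg (88%) | 18 days at 600; 11,400 µg (73%) |
| Step waits for cycle 2: (28 − H) × 200 | 0 days at 600; 5,000 µg (32%) | 0 days at 600; 4,200 µg (27%) |

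**3. Effect on the hold rule if such a subject is counted.** Mass per unit width (under / target / over):
- 2 of 4: 0.29 / 1.13 / 1.19, hold. 2 of 5: 0.49 / 1.65 / 1.03, continue.
- 3 of 6: 0.17 / 1.04 / 1.24, hold. 3 of 7: 0.28 / 1.50 / 1.12, continue.

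**4. Chance that Table 5-1 triggers a hold within eight subjects.** Exact sequential enumeration, with each outcome known before the next subject enters and the unexposed subject's DLT probability set to 0:

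| Assumed DLT rate at 600 | All exposed | One unexposed among 1–4 | Among 5–6 | Among 7–8 |
|---|---|---|---|---|
| 33% | 0.466 | 0.328 | 0.416 | 0.445 |
| 50% | 0.785 | 0.648 | 0.719 | 0.750 |
| 67% | 0.957 | 0.894 | 0.921 | 0.935 |

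Hand check at 50%, all exposed: P(at least 2 of 4) = 0.6875; a third DLT first reached at n = 6 adds 4/16 × 1/4 = 0.0625; a fourth first reached at n = 8 adds 9/64 × 1/4 = 0.0352; total 0.785. One unexposed among the first four: P(at least 2 of 3) = 0.5, plus 3/8 × 1/4 = 0.0938, plus 7/32 × 1/4 = 0.0547, total 0.648.

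**5. Effect on the 10-subject figure.** With one of ten never at 600, the chance of seeing an event at 600 is 1 − 0.9^9 = 0.613 to 1 − 0.8^9 = 0.866, so 61% to 87% against the stated 65% to 89%.

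**The case against.** **The step after CRS need not wait for cycle 2.** The protocol calls the planned rise a dose step. The escalation paragraph in 7.4.2.1.2.4 follows the one on lower-dose restarts, and its 48-hour stay matches the line on re-escalation in 7.1.1.4.1. It is best read as return to dose after a reduction. Section 7.1.1.2 together with the running day count can support a step within cycle 1. This stands. A reader might infer that every run-in hold leads to zero exposure at 600; for CRS the text leaves it open.

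**The model text points to dose received.** Protocol 10.3 and SAP 3.3 update the posterior for a dose level with data from subjects treated at that level. This is a fair argument for excluding an unexposed subject, but the evaluability definitions, the replacement rule and Table 5-1 do not carry it through.

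**Four weeks on treatment could mean on-drug time**, so a held subject has not completed the period. The wording allows it. The running day count and a non-evaluable rule limited to discontinuation favour a calendar window. The SAP's 28 days date DLT events and do not by themselves define evaluability.

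**Many holds do not lead here.** A grade 2 infusion reaction can resume once symptoms have been gone for 30 minutes. Grade 3 CRS at the run-in dose and TLS of grade 3 or more mean discontinuation. For grade 2 TLS, any wish to escalate goes to the medical monitor. That last rule also answers a tempting reading of the next-lower-dose wording as telling sites to go from 200 to 400: it is unclear wording, not such an instruction.

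**Safeguards exist and the event is probably rare.** All first-in-human CRS below 800 µg/day was grade 1. The medical monitor is consulted before a restart after grade 2 CRS, the DLRT reviews the first three subjects dosed at 600 for a full cycle, and safety review is ongoing. These lower the risk but fix neither the step day nor the denominator.

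**Conclusion.** The point holds and is minor. The definitions make a cohort 2 subject evaluable with no 600 µg/day exposure, and the grade 0-to-2 neurologic route leads there under the stated restart rules. The grade 2 CRS route is an ambiguity about when the step occurs.

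If one such subject is among the first four counted, the chance of a hold falls by 0.14 at assumed DLT rates of 33% and 50%, and by 0.06 at 67%. If that subject is seventh or eighth, the loss is 0.02 to 0.04. These sizes rest on assumed DLT rates, since the documents give none for 600, and on a run-in hold having occurred, whose frequency is also not given. They further assume that the subject is counted under cohort 2's nominal dose; neither document states an as-received rule for DLT reporting.

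A reader might infer that the 600 DLT rate will be diluted. The documents show only that the rules permit it.

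**What to change.** **Evaluability (the main change).** In protocol 7.4.1 and 5.2.1 and SAP 6.2, treat a cohort 2 subject with no 600 µg/day exposure in the DLT window and no DLT as non-evaluable for the 600 hold rule and DLT rate, and as replaceable. Continue to report that subject's safety data. Excluding and replacing the subject restores the all-exposed hold probabilities.

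**Step timing (a clarification).** In 7.1.1.2 and 7.4.2.1.2.4, state that where restart at 200 is not a mandated reduction, the step to 600 follows completion of the 3-day run-in. Move the step premedication and the Table 12-4 step monitoring to the actual step day.

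**Cost.** A few sentences and a possible replacement subject. After a minimum 72-hour hold the step moves from hour 72 to hour 144. Keeping 72 hours of observation after it gives 216 hours, a cycle 1 stay of 9 days instead of 6. Amendment 5 cites termination of the program and no further drug supply; if cohort 2 no longer enrols, the SAP 6.2 sentence alone suffices.

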#### **7.4.2.1.2.2 Infusion Interruptions Due to Adverse Events**

Events occurring during the 4-week infusion period of a treatment cycle and requiring treatment interruption will be managed by infusion interruption.

Any treatment interruption due to an adverse event, independent of the duration of the interruption, should be documented on the eCRF including start and stop date/time of the infusion.

#### Delay of Subsequent Infusion due to Adverse Events

Events occurring after the end of the infusion and requiring a delay of treatment will be managed by delay of the subsequent infusion. The site should record any delay of an infusion on the eCRF and provide the start and stop date/time of the infusion.

Events requiring a delay of the subsequent infusion are listed in [Table 7-1](#). Infusion interruptions or delays **greater than 7 days** for other reasons need to be discussed with the Amgen Medical Monitor. **Delays of treatment cycles beyond 14 days are not permitted.**

Events requiring an infusion interruption including guidance for management, re-start, and permanent discontinuation are listed in [Table 7-1](#) and [Table 7-3](#).

---

#### 7.4.2.1.2.3 Re-Start of Infusion

Re-starting treatment after interruption due to an adverse event should be performed in the hospital under medical supervision. Premedication as described in [Section 7.1.4](#) must be administered prior to re-start, if applicable.

The assessments that should be performed as for cycle 1 days 1, 2, and 3 are specified in the Schedule of Activities (see [Section 2.2](#)):

The subject should be hospitalized for at least 48 hours after re-start of the infusion (see also [Section 7.1.1.4.1](#)).

#### 7.4.2.1.2.4 Dosage Adjustments/Re-Start at a Lower Dose Level/ Dose-Escalation

For adverse events for which re-start of treatment is allowed according to the guidelines outlined in [Table 7-1](#) and [Table 7-3](#), treatment may be resumed under medical supervision at the same dose or a lower dose.

Premedication as described in [Section 7.1.4](#) must be administered prior to re-start, if applicable.

##### Re-start at a lower dose level:

If clinically indicated per the guidance provided in [Table 7-1](#) and [Table 7-3](#), treatment will be resumed at a lower dose level (ie, 200 µg/day for subjects originally receiving 400 µg/day or 400 µg/day for those originally receiving 600 µg/day) and continued until the pre-scheduled end of the cycle.

The assessments that should be performed as for cycle 1 days 1, 2, and 3 are specified in the Schedule of Activities (see [Section 2.2](#)).

The subject should be hospitalized for at least 48 hours after re-start of the infusion (see also [Section 7.1.1.4.1](#)).

Only one dose de-escalation step per subject is allowed in the study. In case an additional dose de-escalation is required for a subject, permanently discontinue treatment.

##### Dose-escalation:

Dose-escalation is allowed with start of the next treatment cycle if treatment is well tolerated and escalation is appropriate according to the investigator's judgement. In addition to the assessments required as per Schedule of Activities (see [Section 2.2](#)), a

neurological examination should be performed before dosing in case the infusion interruption was due to a neurologic event.

The subject should be hospitalized for at least 48 hours after dose-escalation (see also [Section 7.1.1.4.1](#)).

**Table 7-1. Infusion Interruptions/Permanent Discontinuations and Management of Adverse Events Including Dose Reductions**

	Interruption	Specific Management	Re-Start Guidance	Permanent Discontinuation
Infusion-related Reaction				
Grade 1	n/a	
 
Consider supportive medication according to local standard of care.
 
Increase monitoring of vital signs as medically indicated.
 
	Continue infusion	n/a
Grade 2	Immediate interruption until event has improved to grade $\leq 1$	
 
Consider supportive medication according to local standard of care.
 
Increase monitoring of vital signs as medically indicated.
 
	
 
Resume infusion at half the previous rate when symptoms have resolved for at least 30 minutes, observe patient and re-escalate to basal rate after 60 minutes if successfully managed and improvement to grade <math>\leq 1</math> in <math>\leq 14</math> days.
 
Hospitalization: 48 hours for start of next infusion
 
Dose modification: resume at the same dose OR consider reducing to next lower dose if clinically indicated (ie, 200 <math>\mu\text{g}/\text{day}</math> for subjects originally receiving 400 <math>\mu\text{g}/\text{day}</math> or 400 <math>\mu\text{g}/\text{day}</math> for those originally receiving 600 <math>\mu\text{g}/\text{day}</math>)
 
Additional measures: additional assessments and premedication as indicated in Sections 7.4.2.1.2.3 / 7.4.2.1.2.4
 
	If interruption is $> 14$ days

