#### 7.4.2.1.2.5 Specific Guidance for Cytokine Release Syndrome

Cytokine release syndrome is clinically defined and may have various manifestations.

There are no established diagnostic criteria. Signs and symptoms of CRS may include:

- constitutional: fever, rigors, fatigue, malaise
- neurologic: headache, mental status changes, dysphasia, tremors, dysmetria, gait abnormalities, seizure
- respiratory: dyspnea, tachypnea, hypoxemia
- cardiovascular: tachycardia, hypotension
- gastrointestinal: nausea, vomiting, transaminitis, hyperbilirubinemia
- hematology: bleeding, hypofibrinogenemia, elevated D-dimer
- skin: rash

Subjects may be at an increased risk for CRS during the first few days following the initial infusion of AMG 420. Cytokine release syndrome may be life-threatening or fatal. Infusion reactions may be clinically indistinguishable from manifestations of CRS. Throughout the treatment with AMG 420, monitor subjects for clinical signs (eg, fever, tachycardia, dyspnea, tremors) and laboratory changes (eg, transaminase increase) which may be related to CRS.

Grading and management of CRS should be performed according to the guidelines provided in [Table 7-3](#) (based on the adopted grading system referenced in [Lee et al, 2014](#)).

Please also refer to the general guidance for re-start of infusion after interruption due to adverse event in [Section 7.4.2.1.2](#)

For grade 3 and 4 CRS, please also see [Section 7.4.1](#) for DLT considerations.

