9.6.2 Adverse Events

The Medical Dictionary for Regulatory Activities (MedDRA) version 23.0 or later will be used to code all adverse events to a system organ class and a preferred term. The severity of each adverse event will be graded using CTCAE version 5.0 criteria with exception of CRS which will be graded according to adopted grading system in Lee et al, 2014 and TLS graded according to Cairo-Bishop criteria (refer to protocol Appendix 12). Where appropriate the tables will also be presented by worst grade.

Treatment-emergent adverse events will be summarized based on the number (%) of subjects experiencing events by MedDRA SOC and PT. The denominator for the percentage will be based on the number of subjects in the safety analysis set.

The subject incidence of adverse events will be summarized for

- **TEAE**
 - All treatment-emergent AEs
 - Grade 3 or higher treatment-emergent AEs
 - Treatment-emergent SAEs
 - Treatment-emergent AEs leading to interruption of investigational product
 - Treatment-emergent AEs leading to withdrawal of investigational product
 - Fatal treatment-emergent AEs
- **Treatment-related AEs**
 - All treatment-related AEs
 - Grade 3 or higher treatment-related AEs
 - Treatment-related SAEs
 - Treatment-related AEs leading to interruption of investigational product
 - Treatment-related AEs leading to withdrawal of investigational product
 - Fatal treatment-related AEs

The summaries that are displayed by SOC, PT and grade will be ordered by descending order of incidence of SOC, PT and grade with in each SOC for the total group.

Then summary of TEAEs, summary of TEAEs, TESAEs, Treatment-related TEAEs, and Treatment-related SAEs by SOC, PT and Grade will be generated for extramedullary subjects.

The above adverse event tables will not be created if two or fewer subjects experience the adverse event.

Dose Limiting Toxicities

The analysis of the probability of DLTs will include data from DLT-evaluable subjects (see Protocol Section 7.4.1 for definition of DLT-evaluable). The primary analysis will only include DLTs that occur during the DLT evaluation period. If DLTs occur outside the DLT evaluation period, a sensitivity analysis will be performed where DLTs occurring outside of the specified time interval are included. The number and percentage of subjects reporting DLTs will be evaluated overall and by AMG 420 dose level.

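### Infusion-related reaction and CRS carry different hold, restart and discontinuation rules at grade 2 and 3, the protocol concedes the two may not be separable, and nothing says which governs an event that fits both.

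*Protocol*

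**What the plan says.** On CRS, Protocol Section 7.4.2.1.2.5 says: "There are no established diagnostic criteria". It then adds: "Infusion reactions may be clinically indistinguishable from manifestations of CRS".

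The two labels are graded and managed separately. Section 7.4.2.1.2.1 applies CTCAE version 5.0 to adverse events "with the exception of CRS, which must be graded using the criteria referenced in the publication by" the authors cited for Table 7-3. TLS has its own scale too; infusion-related reactions stay on CTCAE.

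For a grade 2 infusion-related reaction, Table 7-1 interrupts the infusion and then says: "Resume infusion at half the previous rate when symptoms have resolved for at least 30 minutes". The basal rate follows after a further 60 minutes if the event is controlled. For grade 2 CRS, Table 7-3 interrupts until the event is grade 1 or lower, "but for no less than 72 hours". Its restart column says: "Consult with Amgen medical monitor first". Its discontinuation column includes: "If there is no improvement to CRS ≤ grade 1 within 7 days".

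On the analysis side, SAP 9.6.2 says: "Treatment-emergent adverse events will be summarized based on the number (%) of subjects experiencing events by MedDRA SOC and PT". It adds presentation by worst grade where appropriate, tables of grade 3 or higher, serious, related, interruption and withdrawal events, and a rule that tables are not produced when no more than two subjects have the event. It defines no category combining CRS with infusion-related reaction.

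**The concern.** The protocol recognises one clinical picture that two labels can describe, then makes the hold, the consultation, the dose change and the discontinuation limits depend on the label chosen. Two investigators facing the same event could each follow the text correctly and treat the subject differently.

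The primary objective is safety and tolerability at 400 and 600 µg/day, and CRS is the only important identified risk in Table 3-1. If the label is partly arbitrary, so are the re-exposure decision and the split of events between two rows of the safety tables.

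**Working it through.** **Step 1. The rules side by side.**

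| Item | Infusion-related reaction (Table 7-1) | CRS (Table 7-3 and Section 7.4.2.1.3) |
|---|---|---|
| Grading scale | CTCAE 5.0 | Scale in Table 7-3 |
| Grade 1 | Infusion continues | No interruption |
| Grade 2, earliest restart | 30 minutes after symptoms resolve, at half rate | Grade 1 or lower, and at least 72 hours after interruption |
| Grade 2, medical monitor | Not listed | Consulted first |
| Grade 2, discontinue | Interruption over 14 days | Not grade 1 or lower within 7 days; interruption over 14 days; repeat grade 2 despite dose reduction |
| Grade 3, dose | Reduction mandatory | Restart as for grade 2, where reduction is to be considered after two consecutive grade 2 events |
| Grade 3, discontinue | Interruption over 14 days; more than 2 occasions | Not grade 2 or lower within 5 days and grade 1 or lower within 7; two separate events; interruption over 14 days; any grade 3 at the run-in dose of a dose step |
| Grade 4 | Permanent discontinuation | Permanent discontinuation |

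The labels differ at grades 2 and 3. Neither is stricter throughout: CRS has the longer minimum hold at grade 2, while infusion-related reaction has the mandatory dose reduction at grade 3. The reader therefore cannot infer a rule of taking the more cautious label.

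**Step 2. Is there a tie-break?** Table 7-1 sends CRS to Table 7-3 but does not address an event that might be either. Section 7.8.2.1 refers to Sections 7.4.2.1.2.2 and 7.4.2.1.2.5 for both conditions. The first of these points back to both tables, and the second contains the statement that the two may not be distinguishable. No section says which table or scale governs.

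**Step 3. What the labels share.** Section 7.4.2.1.2.3 requires restart in hospital, with at least 48 hours' stay, after any adverse-event interruption. Section 7.4.1 counts non-hematologic events of grade 3 or higher in the evaluation period as DLTs; neither CRS nor infusion-related reaction is among the listed exceptions. Section 7.4.2.1.3 then requires discontinuation for a DLT unless there is clear benefit, resolution and sponsor consultation. A grade 2 event is not a DLT by the grade criterion under either label.

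**Step 4. Size for the infusion.** Section 7.4.2.1.2.1 keeps the cycle-day count running during an interruption, so missed time is not made up. A 72-hour hold removes 3 of 28 infusion days, 3/28 = 10.7%; at 400 µg/day that is 3 × 400 = 1,200 µg of 28 × 400 = 11,200 µg. For the infusion-related reaction the hold is symptom duration plus 30 minutes, and the documents do not give symptom duration. No comparable figure can be computed.

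**Step 5. Size for the reported incidence.** The first-in-human CRS figure reproduces: 10/35 = 28.6%. In this trial one relabelled subject moves the CRS incidence by 1/10 = 10 percentage points within a cohort and 1/20 = 5 points overall, at any grade. As an illustration with assumed counts and exact 95% intervals: 3/10 = 30% (6.7% to 65.2%) becomes 2/10 = 20% (2.5% to 55.6%) or 4/10 = 40% (12.2% to 73.8%).

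**The case against.** The strongest reply is that the conflict is narrower than it looks.

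- **The minimum holds.** A reader might divide 72 hours by 30 minutes, or conclude that a subject could be re-infused within the hour. The 30 minutes runs from symptom resolution and the 72 hours from interruption. A slow infusion-related reaction could also stay off drug for a long time. This objection stands, and no ratio should be quoted.
- **The same grade on both scales.** CTCAE 5.0 wording is not in the documents, and Table 7-3 has specific grade 2 thresholds (oxygen requirement, hypotension, organ toxicity). Whether a given event would be grade 2 on both cannot be shown. This stands, but unlinked scales are part of the label dependence.
- **The first-in-human rate.** A reader might take 28.6% to mean that about 3 of 10 subjects per cohort would meet the restart conflict. That rate is any-grade and pooled over 0.2 to 800 µg/day; Section 3.2.2.4 says all CRS below 800 µg/day was CTCAE grade 1, where neither label interrupts. It does not size the restart conflict.
- **Grade 3.** In cycle 1 the DLT discontinuation rule comes before the dose-reduction contrast, under both labels. This stands and limits the contrast mainly to later cycles or to subjects allowed to continue.
- **Reporting.** A relabelled event moves to another row and is not lost; the tables go beyond preferred term; and the DLRT sees all available safety data. This stands. Even so, no planned table shows the two labels together. Read literally, the omission rule could also bite once one syndrome is split: four affected subjects recorded two and two would leave each term at the threshold.

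**Conclusion.** The contradiction is on the face of the protocol: the two labels may be indistinguishable, the rules differ at grades 2 and 3, and no governing rule is stated. As written, the label can decide when a subject is re-exposed, whether the medical monitor is consulted first, and when treatment stops.

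The quantified reporting effect is 10 percentage points of CRS incidence per relabelled subject in a cohort of 10. How many subjects would be relabelled is unknown, and the documents offer no estimate.

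Two larger claims might be inferred and are not supported. One is that the enrollment-holding rule is distorted: grade 2 events do not enter the DLT count by the grade criterion, and whether an event could be grade 3 on only one scale cannot be established here. The other is that the comparison of 400 with 600 µg/day is biased: the cohorts are summarised descriptively, and a spurious difference would need relabelling to differ by cohort. The documents give no evidence of that, although the run-in discontinuation rule for grade 3 CRS applies by design to cohort 2 and to cohort 1 only if a dose step is added.

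**What to change.** 1. **Protocol.** Reconcile the infusion-related reaction rows of Table 7-1 with Section 7.4.2.1.2.5, Table 7-3 and the CRS criteria in Section 7.4.2.1.3. State which table and which grading scale govern an event that meets both descriptions. The clinical choice is the sponsor's.
2. **SAP 9.6.2.** Add one summary, by dose level and worst grade, of subjects with CRS or infusion-related reaction as a combined category, beside the separate terms. Exempt it from the rule that drops tables when no more than two subjects have the event.

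The cost is one protocol clarification and one extra table from data already collected. Amendment 5 records that the program has been terminated, so the protocol edit may have limited prospective use; the combined table keeps its value for reporting.
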